9.2 Setting

9.2.1 Study Population

The study population of this study is people in England who have received at least one dose of the Oxford/AstraZeneca COVID-19 vaccine from January 2021 onwards (the AstraZeneca vaccine arm) or at least one dose of another (e.g. mRNA) COVID-19 vaccine from December 2020 onwards (the Other vaccine arm) and people in England who were not vaccinated with any COVID-19 vaccine during the same time period (concurrent control arm) who will be matched to the vaccinated individuals by age, gender, GP practice (NHS region), and comorbidity (see Section

9.7.1 for a description of matching). Study participants of any age will be considered. For the vaccinated individuals, the study's index date is the date of vaccination of the 1st dose.

Concurrent controls who become vaccinated will be censored at date of vaccination and, then may re-enter the study as newly vaccinated individuals. An appropriate control group will be identified for the booster dose evaluation.

To contextualize, we will describe the impact of SARS-CoV2 on the unvaccinated English population, prior to the availability of COVID-19 vaccines. We will conduct a descriptive analysis of COVID-19 of this historical population of unvaccinated persons in England.

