9.3.3 Other Variables and Covariates

Table 6. Variable categories and data sources

Variables	Categories	Data source	Comment
Age	Different categorizations may be used -12 <50; 50-<65; 65-<70; 70-<80; 80+ -18-<40; 40-<50; 50+; 65+; 70+; 80+	GDPPR	BMI is binary as obese or not using HES, SUS, GDPPR or BMI can be created from weight/height if
Gender	Male/Female	-	available;
Ethnicity	White, Black, Asian, Other, Mixed		
Region	NHS Region	-	
Sociodemographic	Socioeconomic status – Index of Multiple Deprivation (IMD)		
BMI	-Obese (BMI 30+) -Not-obese (BMI <30)		
Smoking	- Current - Past - Non smoker		
Comorbidity	Specific comorbidities known to relate with increased risk of severe COVID- 19 and/or suboptimal vaccine response and/or vaccine contraindication including chronic respiratory disease, chronic kidney disease, chronic heart disease and vascular disease, chronic liver disease, chronic neurological disease, diabetes mellitus, severe mental illness, morbid obesity, asplenia or dysfunction of the spleen, and immunosuppression due to disease or treatment.	ORCIHD, HES and GDPPR	Follow JCVI/Green book list of comorbidities (COVID-19 Greenbook chapter 14a) Using ICD or SNOMED codes to identify comorbidities during the baseline period. For immunosuppressant medications, see Prescribed medication section below.
CMMS	0, and by quartile		Created from specific comorbidities;
Non-COVID-19 vaccination	 Flu vaccination (Y/N) Receive adequate vaccination (Y/N) 	GDPPR	An algorithm will be developed to determine if an individual is adequately vaccinated according to recommended vaccination schedule by age and comorbidity status
Prescription medication	Immunosuppressant vs. not	GDPPR	Prescribed medications at baseline will be grouped into immunosuppressant or not.
LTC /assisted living care facility	Yes/No	Not in any database	To be created for people aged 70+ by comparing their zip codes and LTC

Variables	Categories	Data	Comment
		source	
			address; or vaccination at LTC facility. (ORCHID)
Household composition	Size and age combination.	ORCHID UKHSA VE cohort	Available for 7.2 million subset of ORCHID
Frailty score	eFI grouped into - Mild - Moderate - Severe	Derived from GDPPR	Use an algorithm already developed to derive eFI, only available for population 65years and older. For this sub-group analysis.

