9.5 Study Size

The NHS Digital database comprises data from the national registries of vaccination and hospitalization with linkage to the CMR, lab, and mortality data. It is the largest dataset possible for England and covers all regions. As of early March 2021, near 20 million people in England have been vaccinated with at least 1 dose of any COVID-19 vaccines. According to a recent study in Scotland (Vasileiou et al 2021), the Oxford/AstraZeneca vaccine have been used by the majority of the 75+ years old age group and by a significant proportion of the 60-65- and 70-75-years old age groups.

Based on the preliminary count of the cohort of VE from ORCHID in collaboration with PHE (N=5.4 million), as of 7/4/2021, 42.1% of the population have received a COVID-19 vaccine. Overall, 91% of people 80 years and older, 91% of people 65-79 years old, and 79% of people aged 16-64 years old in risk groups were vaccinated. Of those vaccinated, 38% has received the Oxford/AstraZeneca COVID-19 vaccine, i.e. more than 7 million people. It is expected that almost all of England's COVID-19 vaccination data are included in the NHS Digital databases representing the best option for this type of study. Given a large number of people vaccinated with the Oxford/AstraZeneca COVID-19 vaccine and the use of the national database, the study should have sufficient power to address the study objectives.

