Summary tables of all patient characteristics and end points indicated in section 9.3.2 will be created for both the before and after matching situation to provide insight in population characteristics as well as in errors and missingness. Categorical variables will be checked on meaningful categories and frequencies. It is not anticipated that categories will have too low frequency. Pooling will be considered when the frequency for a category becomes below 1000.

Continuous variables will be summarized in terms of min, max, interquartile range, median and mean to get insight in these variables, but also to provide a first indication of use of same unit across the database and to obtain a first impression about possible transformations needed. Missing values will be considered in detail. If the percentage of missingness is below 10%, complete case analyses will be performed. When exceeding 10%, multiple imputation will be run additionally based on the total dataset.

For each outcome event, the summary tables will present for each study cohort the number of first events, total person-years for the event and number of first events per person-years (rate), the RR and the VE which is calculated as 1 - RR. This will also be provided per age group and per frailty score where further stratification/subgroups are indicated below. Finally, VE will also be provided in shorter periods after dose 1, and between the doses, and presence of comorbidities.

Poisson regression with offset for time at risk will be used to estimate rates using the matched dataset, adjusting for the matching variables and BMI, smoking, prescribed medications, and frailty score, which are known to increase risk of hospitalization and death and are likely associated with vaccination.

Checks on linearity for continuous variables will be performed. In order to evaluate interactions of independent variables with the exposure (i.e. vaccinated/comparator), continuous variables will be categorized and the VE will be tabulated per category. For variables for which the maximum and minimum VE across categories is more than 10% different, interaction effects with the exposure will be taken into account in the Poisson model. For interactions among independent variables that are not the exposure, interaction variables will be created. Forward selection is performed, and interaction variables will be included when the computed VE changes with more than 10%.

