9.7.2 Stratification/Subgroup Analyses

Stratifications/subgroup analyses will be fully detailed in the SAP, and may include:

- Age: <12, 12-16, 16-49, 50-64, 65-69, 70-79, 80+; or 16-39, 40-<49, 50+, 65+, 80+
- Comorbidity
 - o categories of the CMMS
 - specific comorbidities known to indicate high risk for COVID-19 infections and/or suboptimal response to vaccine, in accordance with National guidance from UK Health Security Agency (UKHSA, 2021) or other, including chronic respiratory disease, chronic kidney disease, chronic heart disease and vascular disease, chronic liver disease, chronic neurological disease, diabetes mellitus, severe mental illness, morbid obesity, asplenia or dysfunction of the spleen, and immunosuppression due to disease or treatment.
- Immunosuppressant prescribed medication: current vs. past use, regimen
- Long-term care or assisted living care residents (if possible)

Stratifications/subgroups in the vaccinated population may include:

- Heterologous dosing
- Vaccine dose: people receiving 1 dose only, ≥1 dose, 2 doses, booster/other additional doses
- Intervals after the 1st dose among people receiving 1 dose only: 0-7, 8-14, 15-21, 22-28, 29-35, 36-42, 43-49, 50-70, 71-77, 78-84 days post dose 1, and/or other combinations may be used
- Interval between doses among people receiving 2 (or more) doses: 21 to 41, 42 to 69, 70 to 77, 78 to 84, over 84 days and/or other combinations may be used.
- Vaccine batch number
- Aged over 65 by electronic frailty index (eFI) categories (mild, moderately, and severely frail)

Stratification/subgroups in the population with COVID-19 may include:

- COVID-19 severity
- COVID-19 variant

Subgroup analyses will only be conducted if sufficient events for an outcome within the subgroup allows.

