Characteristics of each comparator group will be compared using t-tests for continuous variables and chi-square tests for categorical variables. Initial exploration of the data will be conducted to guide selection of the appropriate analytic strategy. Inverse probability weighted GEE (Salazar et al., 2016) will be used to model non-linear trends in healthcare service use and costs over time, accounting for missing data, and adjusting for the matching variables and BMI status, smoking status, and frailty score. In the models, the total follow-up period will be divided into time intervals and interval-specific weights calculated as the inverse cumulative product of the probability of being observed up to a given interval using the method of van der Wal and Geskus (2011). Inverse probability weighting ensures that observations with a high probability of being missing (for example costs incurred in the later months of follow-up) are given more weight than observations with a low probability of being missing (for example costs incurred in the earlier months of follow-up) (Glick et al., 2015).

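### The all-age VE and cost models adjust for a frailty score that the protocol says exists only from age 65, and no rule says how the score enters below that age.

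*Protocol*

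**What the plan says.** **The model.** Section 9.7.1 estimates rates by Poisson regression on the matched dataset, "adjusting for the matching variables and BMI, smoking, prescribed medications, and frailty score". The frailty term carries no age limit. The synopsis gives the same list. The GEE for resource use and cost in section 9.7.6.2 is fitted "adjusting for the matching variables and BMI status, smoking status, and frailty score".

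**The population.** Section 9.2.1: "Study participants of any age will be considered". The primary objective asks for VE overall and by age group, and the bands in section 9.7.2 include several below 65.

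**The covariate.** Table 6 (section 9.3.3) defines the frailty score as the eFI, graded mild, moderate or severe, and says it is "only available for population 65years and older. For this sub-group analysis". Section 9.7.2 likewise lists eFI only as a subgroup of people over 65.

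**The missing-data rule.** Section 9.7.1: "If the percentage of missingness is below 10%, complete case analyses will be performed". Then: "When exceeding 10%, multiple imputation will be run additionally based on the total dataset". No other rule covers absent covariate values in the VE model, and none separates a value that was not recorded from one that does not exist at a given age.

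**The concern.** Below 65 the score is undefined, not unrecorded. A regression that includes it for everyone needs a stated way of handling those people, and the protocol gives none. An analyst who treats the blank as missing and applies the 10% rule obtains two results, neither of which answers the primary objective. The complete-case fit contains nobody under 65, so a figure reported as overall VE describes older people only. The imputed fit assigns frailty grades to younger people from a relation learned only at 65 and over, with no observed value below that age to support or contradict it.

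Other analysts could reasonably do something else, such as add a not-applicable level, fit separate models by age, or drop the term. These choices can give different overall estimates. The choice therefore determines whom the headline VE represents, and it should not be made after the data are seen.

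**Working it through.** The protocol states no figure tied to this point, so there is none to reproduce. The contradiction lies in the text; the arithmetic only shows how many people it touches.

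**Inputs (section 9.5, ORCHID VE cohort, 7/4/2021)**
- Overall: "42.1% of the population have received a COVID-19 vaccine".
- Coverage at 65–79 is 91% and at 80 and over is 91%, so it is 91% at 65 and over whatever the mix of the two groups.
- Coverage under 65 is not given for the whole age group. Call it c, and let s be the share of the cohort aged 65 or over.

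**Source cohort**

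Overall coverage is the weighted mean of the two age groups:

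0.421 = 0.91·s + c·(1 − s), so s = (0.421 − c)/(0.91 − c).

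s is largest when c = 0: s ≤ 0.421/0.91 = 0.463. At least 1 − 0.463 = 53.7% of the cohort was therefore under 65 and had no eFI. This bound needs no assumption about c.

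**People vaccinated by that date**

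The under-65 share of the vaccinated is c·(1 − s)/0.421.

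| Assumed c | s | Under 65, whole cohort | Under 65, vaccinated |
|---|---|---|---|
| 10% | 0.321/0.81 = 39.6% | 60.4% | 0.10 × 0.604/0.421 = 14.3% |
| 20% | 0.221/0.71 = 31.1% | 68.9% | 0.20 × 0.689/0.421 = 32.7% |
| 30% | 0.121/0.61 = 19.8% | 80.2% | 0.30 × 0.802/0.421 = 57.1% |

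Every row exceeds the 10% trigger. The break-even solves c·0.489/(0.91 − c) = 0.0421, which gives c = 0.0383/0.5311, or about 7.2%. For any under-65 coverage above that, more than 10% of the vaccinated lacked a score.

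**Applying the rule literally**
1. Missingness in frailty exceeds 10%, so multiple imputation is added to the complete-case fit.
2. The complete-case fit with frailty in the model keeps only people with an eFI, all of them 65 or over.
3. The imputation model sees no eFI below 65, so every imputed value there is extrapolated.
4. In a stratum wholly under 65, complete cases number zero, and any adjusted estimate rests on extrapolated values alone.

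The cost GEE carries the same contradiction. Its inverse probability weights deal with costs unobserved later in follow-up, not with a baseline covariate that does not exist for part of the cohort.

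**The case against.** The strongest reply is that no section says people under 65 will be deleted or given imputed scores. Table 6 ties eFI to a subgroup analysis, section 9.7.2 uses it only over 65, and the missing-data rule sits in the paragraph on summarising variables. On that reading the adjustment sentence simply lacks a qualifier limiting frailty to ages 65 and over, and the analyst would notice at the first summary table. Section 9.7.1 also announces a SAP that may modify the plan, and coding a covariate is ordinary SAP business.

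Part of this stands. Deletion or imputation is an inference from the rule, not a stated plan. The SAP was not available for this review and may settle the matter. Three graded levels may also imply a not-frail reference, so that gap is minor.

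It does not remove the point. The protocol does not leave the adjustment set open: it names frailty in the synopsis, 9.7.1 and 9.7.6.2 with no age limit. Section 9.7.1 also says that major changes to the primary endpoint analyses would be reflected in a protocol amendment. The presumed qualifier is missing, and more than one repair is possible.

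Two stronger readings are tempting and are not supported. A reader might infer that adjusted VE under 65 cannot be fitted at all. The rule adds imputation above 10%, so a fit would exist, though a poor one; without the frailty term, the matching variables, BMI, smoking and medications remain. A reader might also carry the age split of the general population, say 75–85% under 65, over to the matched dataset. The documents give no such figure, and the matched set follows the vaccinated, who began with the oldest.

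**Conclusion.** The point holds as an unreconciled contradiction in the primary model and the cost model: an all-age adjustment set includes a covariate that the protocol says does not exist below 65. Followed literally, the stated missing-data rule gives an overall VE that is either a 65-and-over estimate or dependent on extrapolated frailty.

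On size, at least 53.7% of the ORCHID source cohort had no score in April 2021. Among those vaccinated by then, the share is about 14% to 57% for assumed under-65 coverage of 10% to 30%.

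These figures describe the source cohort and its vaccinated members at one early date, for all vaccines together. They are not the age mix of the matched dataset or of the Oxford/AstraZeneca arm, which the protocol does not give. The under-65 share would be expected to rise as vaccination reached younger people, and also if older vaccinees failed to find unvaccinated matches, a difficulty section 9.1 anticipates. The direction is therefore clear, but the exact share in the matched set is not established.

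**What to change.** In section 9.7.1, section 9.7.6.2 and the synopsis, state that:
- eFI enters the all-age models nested within age: a not-applicable level below 65, and at 65 and over the eFI grades with not frail as reference;
- models in strata wholly under 65 omit eFI;
- a value undefined because of age is not counted as missing under the 10% rule, and is neither deleted nor imputed. The rule still applies to an eFI that is unrecorded at 65 or over.

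Add the not-frail category to Table 6.

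Where the age bands in the model break at 65, the not-applicable level is absorbed by the bands below 65. The term then amounts to three indicators (mild, moderate, severe) that are zero for everyone under 65 and for the not-frail at 65 and over.

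This is preferable to removing frailty from the all-age models, which would give up the adjustment for people aged 65 and over in the overall VE. Section 9.7.1 itself gives the reason for keeping it: these covariates raise the risk of the outcomes and are likely to be related to vaccination.

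The cost is about one sentence in each of three places and one category in a table, with no new data. It should be settled before the VE models are run.

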3. RESPONSIBLE PARTIES

Name	Professional title	Role in study	Affiliation	Email address

Name	Professional title	Role in study	Affiliation	Email address

4. **PROTOCOL SYNOPSIS**

Background/Rationale: The United Kingdom (UK) is one of the first countries that introduced a mass vaccination campaign for COVID-19 and vaccination of the adult population first focused on the oldest age groups, their carers and health care workers (JCVI, 2020). Three COVID-19 vaccines were licensed and are being used including the Moderna, the BioNTech/Pfizer, and the Oxford/AstraZeneca vaccines. Vaccination with the BioNTech/Pfizer vaccine started in December 2020 and the Oxford/AstraZeneca vaccine started in early January 2021. This study is to primarily assess the effectiveness of the Oxford/AstraZeneca COVID-19 vaccine. Given the known high efficacy of the mRNA vaccines in randomized controlled trials (RCTs) and real-world evidence studies, the study aims also to evaluate the vaccine effectiveness (VE) of other COVID-19 vaccines as a validation of the study's methods. On 16 September 2021 it was announced that Booster doses would be introduced in the UK to address vaccine waning and for groups with a suboptimal response. Little is known about health care resource utilisation (HCRU) and health care costs for those who have had COVID-19 or by individual clinical risk group. The RAVEN study is a retrospective cohort study to assess the real-world effectiveness of the Oxford/AstraZeneca COVID-19 vaccine in England. The study is using linkage of the English national databases on COVID-19 vaccination, testing, medical records, hospitalization, and death. Analyses will examine the effectiveness of one and two doses, and booster or other additional doses if applicable. This study's extension (October 2021) adds a more detailed exploration of VE in risk groups and an evaluation of the HCRU by people with COVID-19 compared with those who are vaccinated.

Research question and objectives:

Primary: To assess the real-world effectiveness of the Oxford/AstraZeneca COVID-19 vaccine among people who receive at least one dose of the vaccine, overall, and by number of doses, by age group, by comorbidity status, by time period after each dose, by interval between doses.

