9.7 Data Analysis

9.7.1 Statistical Methods – General Aspects

A detailed SAP will be developed for this analysis. The SAP may modify the plans outlined in the protocol; any major modifications of primary endpoint definitions or their analyses would be reflected in a protocol amendment. For all study designs, p-values will be quoted to two decimal places, unless they are less than 0.001 (whereby the p-value will be given as < 0.001) or between < 0.005 and > 0.001, in which case they will be stated to three decimal places. Parameter estimates will be reported with 95% CIs. All statistical tests are 2 sided and with a 5% significance level.

A CONSORT 2010 Flow Diagram of the study population detailing each step of the inclusion and exclusion criteria applied will be generated. As indicated in section 9.4, to obtain the most followup data, the primary analysis will include all HES data until 8 weeks prior and all raw hospitalization data (SUS) from 8 weeks to 2 weeks prior database lock. A sensitivity analysis including only HES data, therefore a shorter follow-up for hospitalization, will also be done.

For the concurrent control arm, each week starting from 8th December 2020, we will match all newly vaccinated persons in a 1:1 ratio to unvaccinated controls (Dagan et al, 2021). Newly vaccinated persons will be eligible for inclusion in the study, even if they will have previously been selected as a control. We will match vaccine recipients and controls on variables associated with the probability of both vaccination and infection or severity of COVID-19: age (study defined age bands), gender, general practice, (or NHS Region), and comorbidity as defined by CMMS quartile. We will exact match each week (if feasible). To assess the quality of matching, love plots will be created showing the mean standardized difference between each vaccinated cohort (AstraZeneca or other vaccine cohort) and the comparator cohorts in participants' characteristics. If important differences are observed, the matching criteria will be refined.

The demographic and characteristics of study participants in each vaccine arm and its respective control arm at baseline will be determined during the 12-month period before index date using the measurement closest to index date.

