9.11.2 Adjustment for Multiple Comparisons

With only a small number of comparisons for the VE analysis, no adjustment for multiple comparisons is needed.

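### The 10% rule for exposure interactions ignores sampling error and leaves no overall adjusted VE defined once it fires, and the reason given for not adjusting for multiplicity does not fit the protocol's own list of comparisons

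*Protocol*

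**What the plan says.** Section 9.7.1 defines the effect measure ("the RR and the VE which is calculated as 1 - RR") and fits a Poisson model to the matched data. To look for effect modification, continuous variables are categorised and VE is tabulated by category. The rule for that model is then that where "the maximum and minimum VE across categories is more than 10% different, interaction effects with the exposure will be taken into account". No interaction test, confidence interval or minimum number of events is attached to the rule. Interactions among the other covariates follow a similar threshold: "Forward selection is performed, and interaction variables will be included when the computed VE changes with more than 10" per cent. Neither threshold is stated as points or as a relative change.

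The same section sets the testing convention: "All statistical tests are 2 sided and with a 5% significance level". Section 9.11.2 then states: "With only a small number of comparisons for the VE analysis, no adjustment for multiple comparisons is needed".

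An overall result is planned. The primary objective in the synopsis (Section 4) asks for effectiveness "among people who receive at least one dose of the vaccine, overall, and by number of doses, by age group, by comorbidity status", and further by time after each dose and by dose interval. On tabulation, Section 9.7.1 says: "For each outcome event, the summary tables will present for each study cohort the number of first events, total person-years for the event", together with the rate, RR and VE.

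**The concern.** The gap between the largest and smallest of several estimates grows with their sampling error and with the number of categories, even when the true VE is the same everywhere. A fixed 10% cut-off therefore does different things in different places. Where events are few it can react to noise. Where VE is high and events are many it can pass over a difference that is large on the rate-ratio scale and well beyond chance.

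What is at stake is the form of the model behind the primary result. Once an exposure-by-covariate term is in the model, the vaccine coefficient describes the reference category of that covariate. The protocol does not say how an overall adjusted VE is then obtained. Because the rule is applied to data, it may fire for one outcome and not another, so that adjusted results for hospitalization, ICU admission and death come from differently built models.

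The sentence in Section 9.11.2 compounds this. If readers are told that few comparisons were made, they will read differences between strata with more confidence than the number of strata warrants.

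**Working it through.** The protocol states no event count, power figure or error rate for this rule, so there is no figure of its own to reproduce.

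**Inputs from the protocol.** 1:1 matching, VE = 1 − RR and the 10% threshold (Section 9.7.1); three primary outcomes (Section 9.3.2); two vaccine arms (Section 9.2.1); bands listed in Sections 9.1 and 9.7.2.

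**Assumed, not in the protocol.** True VE of 20% to 80%, and 100 to 1,000 control events per category (up to 10,000 in one example under the objection); equal person-time; independent Poisson counts; the same true VE in every category; 10% read as points.

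**1. Sampling error of one category's VE.** With n control events and n × RR vaccinated events, SE(VE) ≈ RR × √(1/n + 1/(n × RR)). The SE of the difference between two categories is √2 times that.

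| True VE | n | SE(VE), points | SE of difference | 10 points ÷ SE of difference |
|---|---|---|---|---|
| 80% | 100 | 0.2 × √(0.01 + 0.05) = 4.9 | 6.9 | 1.4 |
| 80% | 300 | 2.8 | 4.0 | 2.5 |
| 80% | 1,000 | 1.5 | 2.2 | 4.6 |
| 20% | 1,000 | 0.8 × √(0.001 + 0.00125) = 3.8 | 5.4 | 1.9 |

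So 10 points can be anything from a routine chance gap to an almost impossible one, depending on event counts and VE.

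**2. Chance that the rule fires with no true modification.** Simulated share of runs with maximum VE − minimum VE above 10 points:

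| True VE | Control events per category | 2 categories | 5 categories | 7 categories |
|---|---|---|---|---|
| 80% | 100 | 15% | 60% | 78% |
| 80% | 300 | 1% | 10% | 17% |
| 80% | 1,000 | about 0% | about 0% | about 0% |
| 60% | 1,000 | below 1% | 3% | 5% |
| 20% | 1,000 | 6% | 34% | 51% |

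One thin band is enough: control events of 20, 300, 800, 400, 900 and 1,500 with VE 80% in all six bands give about 50%.

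Read as a relative 10%, the rule fires more often: VE 20%, 5 categories and 1,000 events gives 99.5%.

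**3. Modification that the rule misses.** VE 95% v 86% is 9 points, so it is not flagged on the points reading. The RRs are 0.05 and 0.14, a ratio of 2.8. With 1,000 control events per category:

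z = ln(2.8) / √(1/1,000 + 1/50 + 1/1,000 + 1/140) = 1.030 / 0.171 = 6.0.

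On a relative reading the answer depends on the base: 9/86 = 10.5% triggers, 9/95 = 9.5% does not.

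**4. Number of comparisons.** Per outcome and arm, using the listed bands: 1 overall + 6 age + 4 dose + 10 time after dose 1 + 5 dose interval + 4 CMMS quartiles = 30. Then 30 × 3 primary outcomes = 90 per arm, and × 2 arms = 180. Two items could fairly be dropped. The stratum of at least one dose repeats the overall analysis, and Section 9.1 mentions licensing in children only for the Moderna and Pfizer vaccines, which removes the 12-15 band from the AstraZeneca arm. That leaves 28 × 3 + 29 × 3 = 171. The total still exceeds 100 before the specific comorbidities, variants, batches or all-cause outcomes.

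**The case against.** **Overall VE.** A reader might infer that the study could end without an overall VE. The documents do not support that. The objective asks for it, and the summary tables give RR and VE for every outcome and cohort whatever the interaction step shows. Nor does the protocol say that a reference-category coefficient would be reported as the overall result. The gap concerns only the adjusted overall VE after an interaction has entered. The SAP could fill it, and Section 9.7.1 allows the SAP to modify plans, but the trigger itself is stated in the protocol.

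**Chance.** A reader might also infer that noise will dictate the model. That does not follow. Section 9.5 describes a national database with more than 7 million AstraZeneca recipients, and at about 1,000 control events per category the rule hardly ever misfires at VE 80%. Two partial safeguards exist: pooling is considered for categories with a frequency below 1000 (Section 9.7.1), and subgroup analyses need sufficient events (Section 9.7.2). Neither is tied to event counts for this rule.

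**Multiplicity.** Multiplying the number of strata by 5% to predict false positives would not measure the harm. It counts tests of VE = 0 with every null true, not tests of differences between strata, and the protocol specifies no test of such differences. The Section 9.7.2 list is also a menu of possible subgroups to be settled in the SAP. In a study reporting estimates with 95% CIs, and whose ENCePP checklist answers No on hypotheses to be tested, declining to adjust is defensible. Only the stated reason is wrong.

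**Significance tests instead.** A pure interaction test has the opposite weakness at this scale. With 10,000 control events per category, VE 90% v 88% gives z = ln(1.2) / √(2/10,000 + 1/1,000 + 1/1,200) = 0.182 / 0.045, about 4, for a difference that few would act on. Some regard for magnitude is sensible. This stands, and it shapes the fix.

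**Limited harm.** VE by age and comorbidity is reported anyway, so a false trigger changes the form of the model rather than which strata appear. That is fair.

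**Conclusion.** Three things hold. First, the 10% rule ignores sampling error and is ambiguous between points and relative. With no true modification and a points reading it fires about 60% of the time at VE 80%, 5 categories and 100 control events per category, 10% at 300 and about 0% at 1,000; at VE 20% and 1,000 events it fires 34% of the time. It also passes over a 2.8-fold RR difference with z = 6.0. Second, once an interaction enters, no overall adjusted VE is defined, and model form may differ between outcomes. Third, the premise of Section 9.11.2 does not fit three primary outcomes, two vaccine arms and five stratification factors, which give on the order of 100 or more VE estimates if the listed bands are used.

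The rates rest on assumed event counts and true VEs. The protocol gives none, so it cannot be said which case applies. ICU admission, death, young age bands, short windows after a dose, and all-cause outcomes (where VE may be low) are the most exposed. The change should be made, but nothing here shows that the overall VE is lost or that the large strata are unreliable.

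**What to change.** 1. **Section 9.7.1, overall result.** For every outcome, report the overall adjusted VE from the model without exposure interactions, or standardised over the matched vaccinees, whatever the interaction step shows.
2. **Section 9.7.1, effect modification.** For the modifiers named in the primary objective, report ratios of RRs with 95% CIs, estimated on the log-RR scale, regardless of the result. Let the size of the difference and its CI together decide whether effect modification is claimed, not the raw 10% range alone. If any 10% threshold is kept, including the one in the forward selection, say whether it is in points or relative.
3. **Section 9.11.2.** Replace the sentence. Name overall AstraZeneca VE on the three primary outcomes as the main comparisons. State that all stratum estimates are descriptive, with unadjusted 95% CIs, and give the number of strata. A Holm adjustment across the three main comparisons is optional.

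The cost is wording in two sections, slightly more reporting and more cautious subgroup claims. No further data are needed.
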